13. TECHNIQUES AND TOOLS
14. SAFETY REPORTING
15. MONITORING & AUDITING
16. TRIAL COMMITTEES
17. FINANCE AND FUNDING
18. INDEMNITY
19. DISSEMINATION OF RESEARCH FINDINGS
20. REFERENCES
21. APPENDICES

2. GLOSSARY of Terms and Abbreviations

AE	Adverse Event
AR	Adverse Reaction
ASR	Annual Safety Report
CA	Competent Authority
CI	Chief Investigator
CRF	Case Report Form
CRO	Contract Research Organisation
DMC	Data Monitoring Committee
EC	European Commission
EMRS	Emergency Medical Retrieval Service
GAfREC	Governance Arrangements for NHS Research Ethics Committees
HEMS	Helicopter Emergency Medical Services
ICF	Informed Consent Form
JRMO	Joint Research Management Office
NHS REC	National Health Service Research Ethics Committee
NHS R&D	National Health Service Research & Development
Participant	An individual who takes part in a clinical trial
PI	Principal Investigator
PIS	Participant Information Sheet
PRSI	Pre-hospital rapid sequence induction of anaesthesia and tracheal intubation.
QA	Quality Assurance
QC	Quality Control
RCT	Randomised Controlled Trial
REC	Research Ethics Committee
SAE	Serious Adverse Event
SDV	Source Document Verification
SOP	Standard Operating Procedure
SSA	Site Specific Assessment
TMG	Trial Management Group
TSC	Trial Steering Committee

4. SUMMARY/SYNOPSIS

Short Title	Impact of pre-prepared drugs & equipment for prehospital RSI.
Methodology	Type of study: Randomised control experiment with a cross-over design
Research Sites	Scottish Ambulance Service, ScotSTAR
Objectives / Aims	Compare the effect on time and safety to set up equipment (kit dump), and place an endotracheal tube during a simulated prehospital scenario. Using different equipment configurations for pre-hospital Rapid Sequence Induction of anaesthesia (RSI). The primary outcome on total intervention time (seconds) and secondary outcomes on safety-related incidents and errors, along with degree of cognitive load, satisfaction, and difficulty scores.
Number of Participants/Patients	24 participants forming 12 two person teams (a physician and a paramedic).
Main Inclusion Criteria	
Retrieval Physicians:
 
 • Currently working with the adult retrieval service of ScotSTAR - Emergency Medical Retrieval Service (EMRS). • Greater than 6 months' experience as a consultant physician with EMRS. • Assessed by EMRS to be competent and current at preparing a kit dump for pre-hospital RSI. 
Helicopter emergency services (HEMS) Paramedics:
 
 • Currently working for the Scottish Ambulance Service air ambulance division alongside EMRS. • Greater than 6 months' experience as a HEMS paramedic. • Minimum of 8 years' frontline ambulance experience. • Completed pre-hospital anaesthesia course⁽¹⁾ or equivalent • Assessed by EMRS to be competent and current at preparing a kit dump for pre-hospital RSI. 
REFERENCES:
 
1. Pre-hospital anaesthesia course. GNAAS. https://www.greatnorthairambulance.co.uk/pha/ Accessed January 25, 2018.

Statistical Methodology and Analysis (if applicable)	
Distribution of data will be assessed using normal quartile plots (or an appropriate test).
 
However, we are aware that each of these statistical tests have their own

	
limitations.
 
If data is parametric then: Catagorical data compared using Chi², continuous data compared with Student T.
 
If non-parametric then: Catagorical data compared with Fischer Exact, continuous data compared with Wilcoxon matched-pair signed-rank test.
 
Primary outcome will compare the mean total intervention time to completion of the process by standard practice vs experimental method. p-value will be set at <0.05 for statistical significance.
 
Secondary outcomes of component times (table 1) will compare the mean time to completion of each component by standard practice vs experimental method.
 
Secondary outcome will be measured using 100mm visual analog score, comparing the mean satisfaction, degree of cognitive load by standard practice vs experimental method.

Proposed Start Date	01 December 2016
Proposed End Date	01 July 2017
Study Duration	7 Months

5. INTRODUCTION

Rapid Sequence Induction of anaesthesia (RSI) in any environment is associated with significant risks including hypoxia, hypotension, or failure to secure an airway. Most of these complications are predictable, and the risk can be greatly reduced with appropriate preparation. In controlled environments, for example the induction of anaesthesia for elective surgery, these risks are extremely low. However, in uncontrolled environments these risks are more likely to increase.

A potential source of error in pre-hospital RSI is the preparation of the required equipment and drugs. Pre-hospital time is an essential factor in the initial care of critically injured/ill patients, and is directly related to mortality. Time saving interventions are therefore beneficial.

One of the principal aims of pre-hospital care is to balance the need for appropriate intervention with the need to transport patients to definitive care.

This study will evaluate the effectiveness of a new method of working, having all necessary equipment and drugs prepared and organised prior to the procedure being required, to investigate whether the improved pre-preparation will make this process faster, while still resulting in the safe placement of endotracheal tubes.

6. TRIAL OBJECTIVES

Research Questions:

- Does pre-preparing drugs and equipment for pre-hospital rapid sequence induction of anaesthesia and tracheal intubation (PRSI) impact the time it takes to safely place an endotracheal tube?
- Does pre-preparing drugs and equipment for pre-hospital RSI impact the error rate (safety)?

Objective:

Compare the effect on time and safety to set up equipment (kit dump) and place an endotracheal tube during a simulated prehospital scenario. Using different equipment configurations for pre-hospital Rapid Sequence Induction of anaesthesia (RSI). The primary outcome on total intervention time (seconds) and secondary outcomes on safety related incidents and errors, along with degree of cognitive load, satisfaction, and difficulty scores.

Definitions / Endpoints

- Primary

- Total intervention time (seconds) - defined in this study, from the decision to perform RSI to confirming placement of endotracheal tube (breathing tube) with the measure of end-tidal capnography (concentration of carbon dioxide at the end of an exhaled breath).

- Secondary

- Component times (seconds) - being the time taken for each component of the process (table 1) to include preparation of airway equipment and drug preparation, checklist, drug administration, onset time, tracheal intubation.

- Safety related incidents

- Procedural errors, defined as error in the preparation or use of medications or equipment with the potential to result in harm an unintended/unexpected incident, which led, or could have led to harm. Errors will be counted and classified according to table 2.

- Procedural lapse, defined as a failure to execute an action due to lapse in memory and a routine behaviour being omitted. Lapse will be counted and classified according to table 2

- Degree of cognitive load - Subjective estimate, using a visual analogue scale, of the amount of cognitive work the procedure entailed. Cognitive load will be defined for the participant as the amount of cognitive work/energy required to complete the procedure, including the level of judgements/decisions needing to be made.

7. METHODOLOGY

Inclusion Criteria

Eligible participants are experts in prehospital care, and perform RSI as part of their normal working practice. They will be retrieval consultant physicians recruited from Scotland's National Retrieval Service (ScotSTAR) and Helicopter Emergency Services (HEMS) Paramedics employed by the Scottish Ambulance Service.

Each participant will be emailed an invitation that includes an information sheet about the nature of the study; consenting participants are then enrolled.

Participants will be randomly assigned into 12 teams of two (a physician and a paramedic) using computer randomisation. Each team will be asked to perform an RSI on a mannequin in a simulated pre-hospital setting.

The trial will comprise of a traditional set-up of a drug bag containing all the required drug vials, syringes and labels to prepare for a pre-hospital RSI, and a conventional airway bag holding all the required airway equipment, versus the new experimental set-up using a new method of working, having all necessary equipment and drugs prepared and organised prior to the procedure being required.

Each team will use both set-ups sequentially during the two scenarios, their starting process (standard practice or experimental method) being decided randomly using computer batch randomisation. To reduce exposure bias and training artefact there will be a minimum period of two weeks between the first and the second scenario. The allocation will be conveyed to the participant in sequential-numbered opaque envelopes, and undertaken independently for each participant group to ensure an adequate number of participants in each arm.

Before commencing their assigned arm of the study each team will be briefed on what is needed and provided as much time as required to prepare, and ask questions. A picture of a kit dump will be used to indicate what is required and standardize the briefing.

The time taken to complete the process will be measured and the difference between the two set-ups compared, along with safety, errors, and degree of cognitive load, satisfaction, and difficulty scores received from the participants. It is anticipated that this process will

take approximately 1 hour of each participants' time. To accurately measure the outcomes, filming will be used, solely for review by the investigators, and then destroyed.

The investigator will record:

- Total intervention time (seconds) - defined in this study, from the decision to perform RSI to confirming placement of endotracheal tube (breathing tube) with the measure of end-tidal capnography (concentration of carbon dioxide at the end of an exhaled breath).
- Component times (seconds) - being the time taken for each component of the process (table 1) to include preparation of airway equipment and drug preparation, checklist, drug administration, onset time, tracheal intubation.
- Procedural errors, defined as error in the preparation or use of medications or equipment with the potential to result in harm an unintended/unexpected incident, which led, or could have led to harm. Errors will be counted and classified according to table 2.
- Procedural lapse, defined as a failure to execute an action due to lapse in memory and a routine behaviour being omitted. Lapse will be counted and classified according to table 2.
- The degree of individual cognitive load (ICL), defined as the amount of cognitive work/energy required by the participant to complete the procedure, including the level of judgements/decisions needing to be made will be measured.

Table 1 - definitions of components of time

	
Description
	
Definition

	
Total Intervention time
	
Total time taken, from decision to RSI to the measure of EtCO₂.

Component times
	
Equipment Preparation
	
Total time taken to setup the airway equipment, from touching the airway bag to completing the equipment setup.

	
Drug Preparation
	
Total time to prepare the drugs, from touching the drug bag to completing the preparation of the drugs.

	
Checklist
	
Total time to complete the checklist, from the point of starting the checklist to completing the last sentence of the checklist.

	
Drug Administration
	
Total time taken to administer the drugs, from picking up the syringe to complete administration of Alfentanil, Ketamine and Rocuronium.

	
Drug Onset Time
	
The time it takes for drugs to reach maximal effect, for optimal intubation conditions (60sec), from the administration of Rocuronium to the decision to attempt intubation.

	
Tracheal Intubation
	
Placement of an endotracheal tube into the trachea, under direct laryngoscopy, confirmed by visualising it pass through the vocal cords, by auscultation and by the measure of quantitative EtCO₂

Table 2 Error Classifications

Classification	Definitions	Examples
Error	Procedural error in the preparation or use of medications or equipment with the potential to result in harm	
Medication:
 
 ○ Syringe containing anaesthesia medication labelled incorrectly or not labelled ○ Incorrect medication administered ○ Incorrect dose administered 
Equipment:
 
 ○ Sharps injury ○ Procedure performed not in accordance with SOP (i.e. checklist not used, bougie not used)
Lapse	A failure to execute an action due to lapse in memory and a routine behaviour being omitted.	
Medication preparation:
 
 ○ Same needle used to draw up multiple medications ○ No syringe cap ○ Unsafe sharps management 
Equipment preparation:
 
 ○ Cuff of endotracheal tube not checked ○ Laryngoscope bulb operation not checked ○ No bougie

Exclusion Criteria

Clinicians who have less than 6 months experience working with or alongside the adult retrieval service (EMRS).

Clinicians who have not been assessed by EMRS to be competent and current at preparing a kit dump for pre-hospital Rapid Sequence Induction of anesthesia (PRSI).

[figure not shown]
Study Design / Plan – Study Visits

Eligible participants are experts in prehospital care, and perform RSI as part of their normal working practice. They will be retrieval physicians recruited from Scotland's National Retrieval Service (ScotSTAR) and Helicopter Emergency Services (HEMS) Paramedics employed by the Scottish Ambulance Service.

Each participant will be emailed an invitation that includes an information sheet about the nature of the study; consenting participants are then enrolled.

Participants will be randomly assigned into 12 teams of two (a physician, and a paramedic) using computer randomisation.

Study Scheme Diagram

8. STUDY PROCEDURES

Informed Consent Procedures and Enrollment

All the voluntary participants are consenting adults, each of whom will firstly have received an information sheet pertaining to this study. In accordance with the Data Protection Act 1998. We will follow ethical and legal practice, all information which is collected about the participant during the research will be kept strictly confidential.

Participants will be allocated a unique study reference number and all data collected will be stored under this number, including questionnaire responses. Participants will also be informed, that filming will be used to accurately measure the outcomes which will only be reviewed by the investigators, after which it will be destroyed. Identifiable electronic data will be stored on an NHS computer in a password protected domain. This information will only be accessible to the researcher.

Each of the participants will be briefed on what they will be expected to do during the study, and advised how their anonymised data will be used. The participant is free to withdraw at any stage, and should they decide to withdraw all their data will be destroyed and will not be included in any subsequent publication.

They will be provided time to ask any questions and once they are happy to proceed the participant will sign a consent form prior to starting.

Randomization Procedures

Each participant (physician and paramedic) will be randomly appointed using computer randomisation into a two-person (physician, paramedic) team.

In addition, computer batch randomisation will be undertaken to establish the first process which would be undertaken by the team (standard practice or experimental arm). The allocation will then be conveyed to the participants by means of sequential numbered opaque envelopes. To ensure adequate inclusion of each team to both arms of the study, this process will be undertaken independently for each participant team.

Schedule of Assessment (in Diagrammatic Format)

Simulation	Total Intervention Time	Component time	Safety related incidents		Cognitive load	Difficulty	Satisfaction
			Errors	Lapse			
First	x	x	x	x	x	x	x
Second	x	x	x	x	x	x	x
Measure	Time in seconds		Number of events		100mm analogue scale		

End of Study Definition

Once all the teams have completed both arms of the study.

9. STATISTICAL CONSIDERATIONS

Sample Size for the study.

- Total UK sample size: 24
- Total international sample size (including UK): 24
- Total in European Economic Area: 24

- Sample size for the study.

24 participants forming 12 two person teams.

Statistical explanation for sample size for the study.

- Sample size was calculated using data from observation of prior EMRS practice: in ten consecutive standard PRSI's, measuring 16:03 to 24:28 minutes: seconds, the mean procedural time was 20:03 minutes: seconds and standard deviation of 3:26 minutes: seconds.

- A 20% reduction in procedural time would be considered clinically significant.

- From this information, the sample size needed for the paired t-test to have a 90% chance of detecting a difference in means of four minutes at a level of significance of 5% (two-sided), is 11 samples. To allow for any exclusions the sample size is adjusted to twelve simulations in each arm.

- Method of Analysis

Distribution of data will be assessed using normal quartile plots (or an appropriate test). However, we are aware that each of these statistical tests have their own limitations.

If data is parametric then:

Categorical data compared using Chi², continuous data compared with Student-T.

If non-parametric then:

Categorical data compared with Fischer Exact, continuous data compared with Wilcoxon matched-pair signed-rank test.

- Primary Outcome

- will compare the mean total intervention time to completion of the process by standard practice vs experimental method. p-value will be set at <0.05 for statistical significance.

- Secondary outcomes

- Component times (seconds) - being the time taken for each component of the process (table 1) by standard practice vs experimental method.
- Safety related incidents
 - Procedural errors, will be counted and classified according to table 2 by standard practice vs experimental method.
 - Procedural lapse, will be counted and classified according to table 2 by standard practice vs experimental method.
- Degree of cognitive load - will be measured using 100mm visual analog score, comparing the mean satisfaction, degree of cognitive load by standard practice vs experimental method.

- *Primary Endpoint*

- Total intervention time (minutes: seconds) - defined in this study as starting at the decision to perform PRSI and ending when correct ETT position, confirmed with the

facilitator turning on the EtCO₂ simulation software, in response to visualising chest inflation.

- Secondary Endpoint

- Component times (seconds) - Time taken to complete each of the components of the procedure are presented in table 1.
- Procedural errors, defined as an unintended/unexpected incident, which led, or could have led to harm. Errors were counted and classified according to table 2.
- Individual cognitive load (ICL), defined as the amount of cognitive work/energy required by the participant to complete the procedure, including the level of judgements/decisions needing to be made will be measured. ICL will be measured using visual analogue score (VAS). At the end of each simulation, participants will be asked to record their perceived degree of cognitive load during PRSI on a standard 100-mm line (0-mm representing no cognitive load and 100-mm representing maximal cognitive load) comparing the means with the process by standard practice vs experimental method.

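### The primary analysis of this two-period crossover has no period term, although the protocol itself expects a training artefact between the two scenarios

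*Protocol*

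**What the plan says.** The synopsis (section 4) describes a "Randomised control experiment with a cross-over design". Section 9 gives "24 participants forming 12 two person teams", and section 7 states: "Each team will use both set-ups sequentially during the two scenarios, their starting process (standard practice or experimental method) being decided randomly". Section 7 also recognises learning between the scenarios: "To reduce exposure bias and training artefact there will be a minimum period of two weeks between the first and the second scenario".

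For the primary outcome, section 9 says that the analysis "will compare the mean total intervention time to completion of the process by standard practice vs experimental method", with significance at p < 0.05. If the data are judged parametric, the rule is "continuous data compared with Student-T"; otherwise it is the Wilcoxon matched-pair signed-rank test. The synopsis repeats these choices. Neither place mentions period or sequence. The sample size in section 9 is explicitly for a paired t-test.

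On order, sections 7 and 8 both prescribe computer batch randomisation, without a block size or an intended split. Section 7 says that allocation is "undertaken independently for each participant group to ensure an adequate number of participants in each arm"; section 8 says that "this process will be undertaken independently for each participant team".

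**The concern.** A team may be faster at its second scenario whichever set-up it uses. A gap of two weeks or more may shrink that effect, but the protocol claims only to reduce it. Random order spreads it over the two set-ups but does not take it out of the analysis.

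Two things follow if period is left out:

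- With a balanced order, learning pushes the within-team differences of the two order groups apart. The paired t-test counts that spread as random error, so the interval widens and power falls.
- With an unbalanced order, part of the learning effect is also credited to one of the set-ups.

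The study has only 12 teams, and the allowance for exclusions is one team. The standard crossover analysis removes both problems at almost no cost.

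**Working it through.** **Inputs.** From section 9: SD 3:26 = 206 s, target difference 4 min = 240 s (20% of 20:03 is 0.2 × 1203 = 240.6 s), two-sided 5%, 90% power, n = 11 raised to 12. Assumed: 206 s is the SD of within-team differences (the protocol uses it so), and the second scenario is faster by P = 60, 120 or 180 s (about 5%, 10% and 15% of 20:03).

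**The plan's own figure.** The normal approximation for a paired test gives (1.96 + 1.2816)² × (206/240)² = 7.74, or 9.66 after adding 1.96²/2. Exact noncentral-t power is 90.5% at 10 teams, 93.5% at 11 and 95.6% at 12. The stated 11 therefore stands, with one team to spare. A two-sample test would need 16 per arm (normal approximation) or 17 (exact t), so the calculation is a paired one.

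**Model.** Let D be standard minus experimental time within a team, and δ the set-up effect. Teams starting with standard practice have mean D = δ + P; teams starting with the experimental method have mean D = δ − P.

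- Unadjusted: the mean of all D, with 11 degrees of freedom.
- Period-adjusted: the average of the two order-group means of D, with variance (σ²/4)(1/n₁ + 1/n₂) and 10 degrees of freedom.

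**Balanced order (6:6).** The unadjusted mean is unbiased, but the expected sample variance of D is 206² + P² × 12/11:

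- P = 60: 42,436 + 3,927 = 46,363, SD 215 s
- P = 120: 42,436 + 15,709 = 58,145, SD 241 s
- P = 180: 42,436 + 35,345 = 77,781, SD 279 s

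Power and type I error by simulation (50,000 runs per case):

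| P (s) | Power, unadjusted | Power, adjusted | Type I error, unadjusted | Type I error, adjusted |
|---|---|---|---|---|
| 0 | 95.6% | 95.2% | 5.1% | 5.1% |
| 60 | 94.6% | 95.2% | 4.2% | 5.0% |
| 120 | 91.0% | 95.2% | 2.5% | 5.0% |
| 180 | 83.3% | 95.2% | 1.1% | 5.2% |

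**Unbalanced order.** The bias of the unadjusted mean is P(n₁ − n₂)/12, with n₁ the teams starting with standard practice. It favours the experimental method if more teams start with standard practice, and the reverse otherwise.

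| Split | Bias | P = 60 | P = 120 | P = 180 |
|---|---|---|---|---|
| 7:5 | P/6 | 10 s | 20 s | 30 s |
| 8:4 | P/3 | 20 s | 40 s | 60 s |
| 9:3 | P/2 | 30 s | 60 s | 90 s |

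At 8:4 the unadjusted type I error stays close to 5%; at 9:3 it is 6.7%, 10.3% and 13.6% for the three values of P. The adjusted analysis holds about 5% in all cases.

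How likely such splits are depends on the allocation method. If each team's order were a separate coin toss, 6:6 would occur with probability 924/4096 = 22.6%, and 8:4 or worse with probability 1 − (924 + 2 × 792)/4096 = 38.8%. With blocks that divide 12 evenly, the split is 6:6.

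**Cost of adjusting.** With an even split, adjusted power is 89.6% at 10 teams, 92.9% at 11 and 95.2% at 12, so the 12 planned teams suffice on the plan's own inputs. If the SD of differences is larger (206 s per procedure with within-team correlation 0 or 0.25), power at 12 teams is 73.8% or 85.0% unadjusted without learning, and 73.0% or 84.3% adjusted. The price of the period term stays below one point.

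**The case against.** The best defence is that the plain paired test is valid in the intended design. At 6:6 it is unbiased and conservative, so it adds no false-positive risk. The documents give no learning effect; at 60 s the loss is about half a point, and even at 120 s power stays just above the planned 90%. The participants are experienced, assessed as competent and current, and fully briefed beforehand, which limits learning. A SAP that is not shown could add a period term. All of this bears on the size of the loss. It does not remove the point, because section 9 does name the comparison, the tests and the threshold, and the alternative is better or practically equal in every 6:6 case examined.

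Three stronger readings are tempting and are not supported:

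- A reader might infer that an unpaired t-test is planned. The protocol names Student's t-test without a qualifier, but the sample size is for a paired test and reproduces only as one, and the non-parametric alternative is matched-pair. The fault is a missing word.
- A reader might infer that order is left to chance. Batch randomisation may mean blocks, and section 7 states an aim of adequate numbers in each arm. What can be said is that no 6:6 split is stated and that independent allocation per team or per group leaves the method unclear.
- A reader might take the reference to participant groups to mean that physicians and paramedics are drawn separately, so that two members of a team could start in different arms. Sections 7 and 8 both set the starting process for the team.

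Nor does the protocol say that order was randomised because of learning; it ties the training artefact to the two-week gap.

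**Conclusion.** The point holds as a cheap and worthwhile improvement. The fixed primary analysis omits a factor that the protocol expects. With a 6:6 order the cost is precision alone: nothing without learning, about 4 points of power at 120 s (91.0% against 95.2%) and about 12 points at 180 s (83.3% against 95.2%). Only the last of these falls below the planned 90%. These figures rest on an assumed learning effect and on 206 s as the SD of within-team differences, although section 9 derives it from ten separate standard procedures; with equal SDs the two coincide only at a within-team correlation of 0.5.

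Bias arises only if the realised order is unbalanced, which the wording neither establishes nor rules out. Blocking alone would not fully prevent it: section 8 has a withdrawing participant's data destroyed, and the loss of one team turns 6:6 into 6:5, a bias of P/11 (about 11 s for P = 120 s).

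**What to change.** - **Primary analysis.** Specify a linear model for total intervention time with team, period and set-up, reporting the set-up effect with its 95% CI. This is equivalent to comparing first-minus-second differences between the two order groups and halving the result.
- **Non-parametric branch.** Replace the signed-rank test for the primary outcome by a rank-sum comparison of the within-team first-minus-second differences between the two order groups.
- **Other continuous outcomes.** Wherever Student's t-test is kept, write that it is paired. It should not stand as an alternative for the primary outcome, since it has no period term.
- **Randomisation.** State one team-level order list in blocks giving 6:6, and align the wording of sections 7 and 8.

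The cost is rewording, possibly a regenerated list, and one degree of freedom (10 instead of 11), about 0.5 points of power if there is no learning. The adjusted analysis loses power if the realised order is unbalanced (about 93% at 8:4 and 88% at 9:3), which the 6:6 list avoids. The period term removes learning common to both orders; it does not correct a carry-over that differs by which set-up came first.

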13. TECHNIQUES AND TOOLS

Techniques and interventions

In both arms of the experiment, the clinical team will be asked to perform performed PRSI on a mannequin, *presented within a realistic pre-hospital clinical simulation* (Appendix 3). This included the decision to RSI, and the performance of the procedure according to the services (SOP).

Tools

Following the simulation, participants will complete a questionnaire (100mm analogue scale) measuring cognitive load, satisfaction, and difficulty.

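### Cognitive load, satisfaction and difficulty are scored by 24 people in 12 teams, but section 9 fixes one rule for all continuous data without handling team; a paired test on 24 individual differences gives p-values that are too small if teammates' set-up differences correlate positively

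*Protocol*

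**What the plan says.** **Who is observed.** Protocol section 9 gives the size as "24 participants forming 12 two person teams". Section 7 states that "Each team will use both set-ups sequentially during the two scenarios", and section 8 (Randomization Procedures) says of the starting order that "this process will be undertaken independently for each participant team". The team is therefore the unit that crosses over and is randomised.

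**Who scores.** The scales are filled in by individuals. For cognitive load, section 9 says that "participants will be asked to record their perceived degree of cognitive load during PRSI on a standard 100-mm line". Section 13 adds that "participants will complete a questionnaire (100mm analogue scale) measuring cognitive load, satisfaction, and difficulty".

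**How it is analysed.** Under Method of Analysis, section 9 gives one rule for data judged parametric: "Categorical data compared using Chi², continuous data compared with Student-T". If not parametric, continuous data go to the Wilcoxon matched-pair signed-rank test. For the scales it plans "comparing the mean satisfaction, degree of cognitive load by standard practice vs experimental method", and for cognitive load again "comparing the means with the process by standard practice vs experimental method". Section 9 says nothing about averaging within team, a team effect or the unit of analysis for these scores. Student t is not called paired there, although the sample-size paragraph uses a paired t-test. Difficulty is scored, and section 7 says it will be compared, but the section 9 analysis does not name it.

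**The concern.** The rule suits the primary outcome, which is one time per team and simulation. The VAS scores differ: two people rate the same simulation, on the same occasion, with the same set-up order. A simulation that goes well or badly, or learning between the two occasions, can move both ratings together. The two differences within a team may then not be independent pieces of evidence, yet a paired test on individuals would count them as such.

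At stake is the strength of any claim that the new kit lowers cognitive load or raises satisfaction. These are subjective ratings by users who know which kit they are using. Section 10 discloses that the kit's designers, employed by the ambulance service, receive a royalty on it. A nominal 5% test on such outcomes should really be a 5% test.

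**Working it through.** **The plan's own figure.** The only sample size stated is 11, for total time: paired t-test, 90% power, two-sided 5%, difference 4 min (240 s), SD 3:26 (206 s).
- Normal approximation: (1.960 + 1.282)² × (206/240)² = 7.74.
- Small-sample correction: 7.74 + 1.960²/2 = 9.66, so 10.
- Exact noncentral t: also 10 (power 90.5%; 93.5% at 11).

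The stated 11 is close enough. It counts teams and says nothing about the VAS outcomes, for which the protocol gives no SD, correlation or power.

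**Which correlation matters.** Write a score as team effect + person effect + team-by-set-up effect + residual. In a person's difference between set-ups, the team and person effects cancel. With v_TS the team-by-set-up variance and v_E the residual variance, the correlation between teammates' differences is

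r = v_TS / (v_TS + v_E).

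Only this r enters the paired analysis.

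**Size for a paired t-test on 24 individual differences.** With two people per team, the true standard error exceeds the computed one by a factor of about √(1 + r), and the effective number is 24/(1 + r). Type I error comes from simulation, 200,000 trials per value, of 12 teams of two with no set-up effect. All values of r are assumptions.

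| r | √(1 + r) | 24/(1 + r) | Type I error, 24 individuals | Type I error, 12 team means |
|---|---|---|---|---|
| −0.3 | 0.837 | 34.3 | 2.1% | 4.9% |
| 0 | 1.000 | 24.0 | 5.0% | 5.1% |
| 0.1 | 1.049 | 21.8 | 6.1% | 4.9% |
| 0.2 | 1.095 | 20.0 | 7.3% | 4.9% |
| 0.3 | 1.140 | 18.5 | 8.6% | 5.1% |
| 0.5 | 1.225 | 16.0 | 11.2% | 5.0% |
| 0.7 | 1.304 | 14.1 | 13.9% | 5.0% |

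A separate run agreed to about 0.1 percentage point. The simulations used the t-test; the Wilcoxon test also assumes independent pairs, but its error rate was not simulated.

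**Correlated scores, and paired against unpaired** (100,000 trials each, teammates' scores correlated at 0.5 in every row):

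| Source of the score correlation | r | Within-person correlation | Paired | Unpaired |
|---|---|---|---|---|
| Team effect common to both set-ups | 0 | 0.5 | 5.1% | 0.9% |
| Half common, half team-by-set-up | 0.5 | 0.5 | 11.1% | 2.9% |
| Team-by-set-up only | 0.5 | 0 | 11.2% | 11.3% |

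The paired test is inflated only when r is above 0. The unpaired test can err in either direction.

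**Width of an interval from 12 team means against one from 24 individuals.** Degrees of freedom fall from 23 to 11, so the factor is √(1 + r) × 2.201/2.069 = √(1 + r) × 1.064:
- r = 0: 1.000 × 1.064 = 1.06
- r = 0.2: 1.095 × 1.064 = 1.17
- r = 0.3: 1.140 × 1.064 = 1.21
- r = 0.5: 1.225 × 1.064 = 1.30
- r = 0.7: 1.304 × 1.064 = 1.39

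**The case against.** The strongest reply is that the error is inferred. No sentence says that the VAS analysis has n = 24; averaging to 12 teams is not excluded; and the unit of analysis for a secondary questionnaire is often settled in the SAP. The first two parts stand. A reader might infer that the plan commits itself to 24 independent observations, and the text does not go that far. The third part stands only partly, because the protocol does not leave the test open. It fixes one rule for every continuous outcome and describes cognitive load as an individual measure. Followed literally on the scores as collected, that rule leads to 24 pairs.

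Other stronger readings are also unsupported:
- **Any correlation between teammates' scores does harm.** It does not; a team effect common to both set-ups cancels in the paired test.
- **The false-positive rate does exceed 5%.** The protocol gives no correlation. Physician and paramedic have different roles, so r could be near zero or negative, and the test would then be accurate or conservative.
- **Confidence intervals will be too narrow.** Section 9 plans none. It names only a p-value threshold, and that under the primary outcome.
- **The error has a known direction whatever the test.** Student t is not said to be paired, and an unpaired version could be conservative or inflated.

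**Conclusion.** The point holds in conditional form. Section 9 sets a rule that fits team-level time and does not fit person-level scores. If that rule is applied as a paired test to 24 individual differences, and if teammates' differences between set-ups correlate positively, p-values for cognitive load, satisfaction and difficulty are too small. Over an assumed correlation of 0.1 to 0.7, a nominal 5% test runs at about 6% to 14%; at zero it is correct. How likely each value is cannot be judged from the protocol, though the shared simulation, occasion and order make a positive one plausible.

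The primary outcome is untouched, since total time is one value per team and simulation. This is worth correcting before analysis, but it does not threaten the trial's main conclusion.

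**What to change.** In section 9:
1. State that the t-test is paired.
2. State that, for each VAS, the two teammates' scores are averaged per simulation and the 12 within-team differences are analysed, as for time.
3. Name difficulty among the scales analysed.
4. Show physician and paramedic results separately, as description.

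A mixed model is an acceptable alternative only if it has a team-by-set-up (equivalently team-by-simulation) random effect besides the team and participant effects. Without it the team term cancels from the set-up contrast. In 200 simulated trials with r = 0.5, a model with only team and participant random effects gave the same standard error as the individual-level paired analysis adjusted for period (median ratio 1.000). The type I error of that analysis is 8.7%, 11.5% and 14.4% at r = 0.3, 0.5 and 0.7.

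The cost is wording; no further participants or data are needed. Any interval reported from 12 team means will be wider than one that treats 24 people as independent: by about 6% if r is 0, and by about 17%, 21%, 30% and 39% at r = 0.2, 0.3, 0.5 and 0.7. Apart from the 6% due to fewer degrees of freedom, that extra width is uncertainty that the individual-level analysis would leave out.
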